## 11.2 Variables of analysis

Primary endpoint is the metabolic complete response (CR) in week 18 in patients with initially remaining lymphoma judged by FDG-PET/CT.

Secondary endpoints are:

- Morphologic CR, PR, SD, PD in week 7, week 18 and month 6 in patients with initially remaining lymphoma judged by CT/MRI
- Historical comparison of the morphologic response with MIR data (using MabThera); the comparison of the CR rate in week 7 would be a comparison of the two different CD20 antibodies. Based on the patient numbers no matched pair analysis will be possible
- Progression-free survival (PFS) of all treated patients (2 years after individual treatment start)
- Toxicity (NCI-CTC criteria, version 4.03) of all patients
- Relapse rate and pattern of recurrence of all treated patients at all follow-up visits.
- Overall survival (OS) of all treated patients (2 years)
- Quality of life according EORTC QLQ C30 and FACT-Lym questionnaires at inclusion and in week 18, month 12, 24 and 30 (all treated patients)
- MRD response: initially, week 18, months 12 and month 24 (all treated patients). MRD is evaluated by the laboratory of [name] (Kiel) using at least the markers: t(14:18) PCR for MBR, 3'mbr, 5'mcr and MCR; clonal IGH rearrangements (FR1-3); clonal IGL rearrangements (IGK and Kappa-KDE)

## 11.3 Definition of the Trial Populations

All patients, who received at least parts of the treatment defined in this protocol, will be analyzed in the intention-to-treat (ITT) population as well as in the safety population. All patients, who deviated less than 20% from the protocol-defined dose and fulfill all inclusion and exclusion criteria, will be analyzed in the per-protocol (PP) population. Efficacy will be evaluated in the ITT- as well as in the PP population. Toxicity data will be analyzed in safety population.

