### Radiation therapy

- Involved site radiotherapy of the involved lymph node regions: 2 x 2 Gy in week 9 on two consecutive days (after 5th administration of Gazyvaro)
- Salvage radiotherapy if there is no metabolic CR **and** morphological PR/CR at week 18: additional 18 x 2 Gy (5x2 Gy/week) starting from week 20 (without Gazyvaro)

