#### 5.5 Criteria of Withdrawal

##### 5.5.1 Withdrawal of patients from treatment

Any patient can withdraw from the treatment at any time without personal disadvantages and without having to give a reason. Patients who discontinue participation in the clinical study on their own or patients who are withdrawn by the investigator, for reasons other than disease progression (i.e. in case of AEs, protocol violations, ...), will be defined as premature withdrawals. Premature withdrawals will not be replaced.

The investigator can also discontinue the study after considering the risk-to-benefit ratio, if he/she no longer considers the further treatment of the patient according to study protocol justifiable. The date of and the primary reason for the withdrawal, as well as the observations available at the time of withdrawal are to be documented on the CRF. Reasons leading to the withdrawal of a patient can include the following (**one primary reason must be determined**):

- **Lack of efficacy** of the study medication, e.g.
  - Progress of study disease compared to baseline
  - Need for a prohibited concomitant medication for the treatment of study disease
- **Intolerable adverse events**
- **Lack of patient's cooperation**, e.g.
  - Patient's request to withdraw
  - Lack of compliance, patient fails to attend the interim visits as agreed
  - Existing or intended pregnancy, lactation
- **Other reasons** (noting reason), e.g.
  - Other diagnosis than study disease
  - Did not meet major in-/exclusion criteria (coming to light after inclusion)

In all patients who finish the study prematurely, a withdrawal examination at least with respect to the primary endpoint should be carried out. The patient must be asked to consent to this last examination. The withdrawal examination must be documented in the CRF.

In case of a drop-out, all ongoing AEs or SAEs should be monitored until there are no more signs or symptoms or until the participant shows a stable condition.

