# 11. STATISTICAL PROCEDURES

## 11.1 Number of Patients

Due to the descriptive character of the trial, no assessment of any formal statistical hypotheses is performed. The calculation of the number of patients is primarily based on the aspects of practicability and precision of the results. The following calculations are based on the intention-to-treat (ITT) population. Since the strength of the results for the primary endpoint may be weakened due to early drop-outs (as described later), the number of patients needed should be high enough to compensate for potential drop-outs. Primary endpoint is the rate of metabolic CR in week 18 in patients with initially remaining lymphoma judged by FDG-PET/CT. Based on the morphologic CR rate of 37-84% after 2 x 2 Gy in the literature (see Table 2) and in face of a lack of data for metabolic CR after 2x2 Gy, a CR rate of 60% (about the median of CR in Table 2 and approximately the CR rate in week 18 in the MIR

trial (62%)) is assumed. If fifty patients enter the FDG-PET/CT and the observed metabolic CR rate amounts to 60%, the half width of the asymptotic two-sided 95% confidence interval amounts to about  $\pm 13.5\%$ .

Based on the experience of the MIR trial, a general drop-out rate of 10% is assumed, and about 30% of the included patients are expected to have no remaining lymphoma after initial surgery to prove the histology. In addition, we expect an additional drop-out rate of about 15% after the initial FDG-PET due to stage-shifting in a stage III disease based on the Barrington paper about PET staging [45].

These considerations lead to the following calculation:

If 93 patients are being recruited, about 15% will drop out due to a stage-shift to higher stages after FDG-PET (79 patients remaining). Of these 79 patients, about 30% will have no remaining PET-positive lymphoma after initial surgery (according to the experiences in the MIR trial). Therefore, 55 patients would start therapy with the goal of reaching the primary endpoint assessment. Assuming a drop-out rate of 10%, 50 patients will be available for final assessment of the primary endpoint.

The number of  $n=93$  is at the upper limit of the patients to be included. This number of definitively included patients might drop during the trial (e.g. if less patients show a stage-shift or more patients show remaining lymphoma).

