## 11.4 Statistical Methods

There will be a descriptive analysis of the data. The rate of metabolic CR in week 18 will be calculated as relative frequency. The related 95% confidence interval will be calculated using the "score method" by Wilson [65]. This method showed excellent performance characteristics as compared to alternative

approaches of constructing confidence intervals for rates [64]. In addition, the rate of metabolic CR will be estimated using the Kaplan-Meier method and the 95% Greenwood confidence interval to take into account a potential influence of censored values. (ITT and PP population)

PFS and OS at 2 years after initiation of the therapy of each patient will be analyzed using the Kaplan-Meier method and the two-sided 95% confidence intervals according to Greenwood. (ITT and PP population).

Remission- and recurrence rates will be calculated as relative frequencies and reported together with the 95% confidence intervals according to Wilson. (ITT and PP population)

Quality of life will be evaluated according to the evaluation guide of the two questionnaires. (ITT and PP population)

Toxicity will be evaluated for frequency and intensity (safety population). Adverse events will be coded by MedDRA (actual version at the time of data base lock). The counts of the events and the counts of patients will be listed in a table. All patients under observation will be taken into account for the calculations of the frequency of recurrences at the respective time.

All statistical procedures will be defined in a statistical analysis plan (SAP), which will be finalized before data base lock. The responsible statistician and the LKP will authorize the SAP.

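### The per-protocol dose rule names no dose and has no week-18 cut-off; if salvage radiotherapy counts, PP membership depends on the primary outcome

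*Combined protocol and SAP*

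**What the plan says.** Section 11.3 defines the PP set by two conditions: "All patients, who deviated less than 20% from the protocol-defined dose and fulfill all inclusion and exclusion criteria". It adds: "Efficacy will be evaluated in the ITT- as well as in the PP population". It does not say whether the dose is that of the antibody, the week-9 low-dose irradiation, the salvage irradiation or some combination. No date closes the assessment of dose.

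Section 11.2 states: "Primary endpoint is the metabolic complete response (CR) in week 18 in patients with initially remaining lymphoma judged by FDG-PET/CT". Section 11.4 states: "The rate of metabolic CR in week 18 will be calculated as relative frequency". A Wilson interval goes with it, in both the ITT and PP populations. Section 11.4 applies the same two populations to PFS, OS, remission and recurrence rates and quality of life.

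The Synopsis (Radiation therapy) prescribes "Salvage radiotherapy if there is no metabolic CR", joined to a condition on morphological response, with 18 x 2 Gy starting in week 20. Section 4.1 lists this course within the initial therapy phase, marked as conditional. Section 7.1 asks for a treatment plan covering 40 Gy in 20 fractions, to be reused for salvage.

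The documents differ on who is due salvage. The Synopsis, Section 3 and Section 7.3 include a patient with metabolic CR who lacks a morphologic PR or CR. Section 1.2 (Role of FDG-PET) goes by the PET result alone. Footnote 6 of the Study Schedule refers to a positive PET but also mentions morphologic response.

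Section 5.5.1 lists "Progress of study disease compared to baseline" among the reasons for withdrawal.

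**The concern.** A PP set for a week-18 endpoint should depend only on what happened before that endpoint was measured. Salvage comes afterwards and is assigned because of the result. If it counts toward the dose, a patient without metabolic CR who declines or shortens salvage leaves the PP denominator, while most patients with metabolic CR face no such test. Failures are then removed preferentially, and the rate rises for a reason unrelated to how well the study treatment was delivered before week 18.

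A second route does not need salvage to count. On any reading that includes the antibody dose, a patient taken off treatment early for progression can breach the 20% limit and leave the PP set, although that patient is a treatment failure.

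At stake is one of the two planned estimates of the primary endpoint. A PP rate above the ITT rate could be read as the benefit of adequate treatment when part of the gap is selection on the outcome.

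**Working it through.** **Inputs.** From Section 11.1: assumed CR rate 60% and "50 patients will be available for final assessment of the primary endpoint". From Sections 7.2 and 7.3: 2 x 2 Gy in week 9, then 18 x 2 Gy salvage. From the Synopsis: 7 antibody infusions. The number of salvage-due patients who miss the dose limit is not in the documents, so it is varied below as an assumption.

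**The plan's own figure.** Half width = 1.96 x sqrt(0.6 x 0.4 / 50) = 13.58 points, against about 13.5 stated. The recruitment chain also reproduces: 93 x 0.85 = 79.05; 79 x 0.70 = 55.3; 55 x 0.90 = 49.5. The plan gives no PP figure.

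**Who would leave the PP set on the radiation dose, if salvage counts.**
- No salvage: 4 of 40 Gy received, a 90% shortfall. The patient is out.
- 14 of 18 fractions: 8/36 = 22.2% of the salvage dose, or 8/40 = 20% of the total. The patient is out on either count, because the deviation must be below 20%.
- 15 of 18 fractions: 6/36 = 16.7%, or 6/40 = 15%. The patient stays in.

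**Effect on the PP rate.** At 60% of 50 there are 30 metabolic CRs and 20 non-CRs. If k of the 20 fall short, the PP rate is 30/(50 - k).

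| k (assumed) | PP rate | Wilson 95% CI | Shift in points |
|---|---|---|---|
| 0 | 60.0% | 46.2 to 72.4 | 0 |
| 2 | 62.5% | 48.4 to 74.8 | +2.5 |
| 4 | 65.2% | 50.8 to 77.3 | +5.2 |
| 6 | 68.2% | 53.4 to 80.0 | +8.2 |
| 10 | 75.0% | 59.8 to 85.8 | +15.0 |

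**Metabolic CRs that are also due salvage.** Suppose 4 of the 30 metabolic CRs lack a morphologic PR or CR (an assumption) and the same shortfall fraction q applies to everyone due salvage. The PP rate is (30 - 4q)/(50 - 24q). For q = 10%, 20% and 30% this is 62.2%, 64.6% and 67.3%, slightly below the 62.5%, 65.2% and 68.2% in the table.

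**Other CR rates.** With metabolic CR rate c, salvage due to non-CRs only and a 20% shortfall among them, the PP rate is c/(c + 0.8(1 - c)). At the ends of the range in Section 11.1, 37% becomes 42.3% and 84% becomes 86.8%.

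**Stopping for progression.** One missed infusion is 1/7 = 14.3%, so the patient stays in. Two missed is 2/7 = 28.6%, so a patient stopped after 5 or fewer infusions is out if antibody dose counts. Removing one such patient who had been assessed as non-CR gives 30/49 = 61.2%.

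**The case against.** The strongest reply is that Section 11.3 nowhere says salvage is part of the dose. Section 6.5.1, headed Dosage, concerns the antibody alone, and Section 4.1 marks salvage as conditional. If the rule means the antibody, or only treatment planned for everyone, salvage removes nobody. This stands: a reader might infer that the PP set is defined on the whole course including salvage, but that is one permitted reading and not stated text. It does not remove the point, because the rule allows that reading and the trial is open, so the choice would otherwise be made with outcomes visible.

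A reader might also infer that only non-CR patients are exposed and that the PP rate can only rise. The documents do not support this. Under the Synopsis, Section 3 and Section 7.3, a metabolic CR without morphologic PR or CR is also due salvage. If 2 such patients alone fell short, the rate would drop to 28/48 = 58.3%. Upward bias is the expected direction, not a certainty.

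The shortfall counts are assumptions. The 10% drop-out in Section 11.1 acts before the primary assessment (55 to 50) and says nothing about salvage completion. Likewise, a progressor who leaves before week 18 may already be among those 5, in which case the 30/50 does not change. The 61.2% applies only to progressors who were assessed, which can happen because Section 5.5.1 asks for a withdrawal examination covering the primary endpoint.

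Nor does it follow that agreement between ITT and PP would be uninformative: near-equal rates would suggest little such selection. It is a gap between them that could not be interpreted.

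Finally, Section 11.4 leaves procedures to a later SAP. That is the place to settle details, but the protocol has already fixed the rule without a cut-off.

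**Conclusion.** The point holds in conditional form. The dose criterion in Section 11.3 is undefined and unlimited in time, and the one PP set serves both the week-18 endpoint and later ones. If salvage counts, PP membership depends on the week-18 result and the PP CR rate is expected to be too high. The shift is zero if all salvage is delivered within the limit, and 2.5 to 8.2 points if 2 to 6 of 20 non-CR patients fall short. Against the planned half width of about 13.5 points, that is roughly one fifth to three fifths (2.5/13.5 and 8.2/13.5). These figures rest on 30 CRs in 50, on an assumed shortfall, and on salvage being due to non-CRs only; the check with 4 exceptions changes them by less than 1 point. The loss of early progressors is a smaller, separate problem that arises wherever antibody dose counts.

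A reader might infer that the primary result as a whole is biased. It is not: this rule does not touch the ITT estimate, on which Section 11.1 bases its calculations, and the trial is descriptive with no decision threshold. The exposure is confined to the PP estimate. The change is worth making but is not critical.

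**What to change.** In Section 11.3, and again in the SAP:
- Name the doses that count, and say whether the 20% limit applies to each modality separately or to a combined measure.
- For week-18 metabolic CR, base PP compliance only on treatment due before the week-18 PET: the antibody infusions and the week-9 low-dose irradiation.
- State that stopping because of progression or death is not a dose deviation, so that these patients stay in the PP set as failures.
- Apply any salvage-dose criterion only to a separate PP set for PFS, OS and later outcomes.

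The statements on who is due salvage (Synopsis, Study Schedule footnote 6, Sections 1.2, 3 and 7.3) must also be reconciled, since any salvage-dose criterion depends on them. Which of them applies is for the sponsor to settle.

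The cost is a few sentences. The change to the PP definition needs no new data and alters nobody's treatment. The downside is that the PP rate may look slightly less favourable.

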## 11.4 Statistical Methods

There will be a descriptive analysis of the data. The rate of metabolic CR in week 18 will be calculated as relative frequency. The related 95% confidence interval will be calculated using the "score method" by Wilson [65]. This method showed excellent performance characteristics as compared to alternative

approaches of constructing confidence intervals for rates [64]. In addition, the rate of metabolic CR will be estimated using the Kaplan-Meier method and the 95% Greenwood confidence interval to take into account a potential influence of censored values. (ITT and PP population)

PFS and OS at 2 years after initiation of the therapy of each patient will be analyzed using the Kaplan-Meier method and the two-sided 95% confidence intervals according to Greenwood. (ITT and PP population).

Remission- and recurrence rates will be calculated as relative frequencies and reported together with the 95% confidence intervals according to Wilson. (ITT and PP population)

Quality of life will be evaluated according to the evaluation guide of the two questionnaires. (ITT and PP population)

Toxicity will be evaluated for frequency and intensity (safety population). Adverse events will be coded by MedDRA (actual version at the time of data base lock). The counts of the events and the counts of patients will be listed in a table. All patients under observation will be taken into account for the calculations of the frequency of recurrences at the respective time.

All statistical procedures will be defined in a statistical analysis plan (SAP), which will be finalized before data base lock. The responsible statistician and the LKP will authorize the SAP.

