### Statistical analysis

Trial data are evaluated by applying methods of descriptive data analysis:

Rate of metabolic CR in week 18 after initiation of the therapy of each patient as relative frequency including the two-sided 95% confidence interval according to Wilson. (ITT and PP populations).

PFS and OS at 2 years after initiation of the therapy of each patient will be analyzed using the Kaplan-Meier method and the two-sided 95% confidence intervals according to Greenwood (ITT and PP populations).

Quality of life will be evaluated according to the evaluation guide of the two questionnaires.

(ITT and PP populations).

Toxicity will be evaluated for frequency and intensity (safety population).

[figure not shown]

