 before therapy before each infusion of Gazyvaro Weight, height, comorbidities, medication, physical examination including lymph node status, FLIPI Na, K, AST/ALT, Bilirubine total, AP, creatinine: all baseline-values older than 4 weeks before first Gazyvaro infusion. as described in synopsis Irradiation: Dosage according ICRU 50

Week 9: IS-Radiation Total dose: 4 Gy

Single dose: 2 Gy per day on two consecutive days

Salvage RT on remaining lymphoma (after positive FDG-PET/CT week 18) from week 20 (until week 23 or 24): total dose 36 Gy, single dose 2 Gy, 5 fractions per week

There is no salvage RT in case of metabolic CR and morphologic PR

 Fine needle aspiration is not acceptable. Biopsy specimens should be sent to the reference pathologists as early as possible. Histology must be not older than 6 months TSH, fT3/fT4 in case of cervical involvement MRD-diagnostic via [name]. [name], Kiel differential blood cell count: hemoglobin, leucocytes, thrombocytes, neutrophils, lymphocytes HBV-Testing: at least HBsAG-status and HBcAb-status Hepatitis/HIV screening can be dispensed if values not older than 3 months exists; pregnancy testing in blood serum

 FDG-PET/CT after trial inclusion (initial FDG-PET/CT): it can be dropped if there is an existing FDG-PET/CT not older than 4 months and performed under the requested conditions. (central review of these images in Heidelberg)

 PET/CT in week 18 if there was initially PET positive remaining lymphoma

 Serum electrophoresis: albumin, M-component

 CT/MRI: head/neck, thorax/ abdomen/ pelvis incl. inguinal region), if necessary additional ultrasound. staging procedures not older than 4 months.

 CT of the involved region as planning CT

 in case of salvage RT from week 20

 CT/MRI only, in week 18 in patients with PET negative initially enlarged lymph nodes

 Pregnancy test (serum) in all women with childbearing potential (including tubal ligation)

 Pregnancy test (serum or urine) in all women with childbearing potential (including tubal ligation); In case of a positive urine pregnancy test, dosing will be delayed, until patient's status is determined by a serum pregnancy test.

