### 11.6 Definition of Target Variables

Progression-free survival:

- a) Calculated from start of therapy up to the time of progression (morphologic or metabolic) or death
- b) Calculated from start of therapy up to the time of progression (morphologic or metabolic) or death in patients with initially remaining lymphoma (morphologic or metabolic)

Overall survival:

Calculated from start of therapy up to the time of death

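### The added Kaplan-Meier estimate of week-18 metabolic CR has no event time to work on and does not adjust for missing scans

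*Combined protocol and SAP*

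**What the plan says.** Section 11.2 defines the endpoint as a status at one time: "Primary endpoint is the metabolic complete response (CR) in week 18 in patients with initially remaining lymphoma judged by FDG-PET/CT". Footnote 14 of the Study Schedule provides a single response scan, "PET/CT in week 18 if there was initially PET positive remaining lymphoma", and the schedule allows ±1 week around it.

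For the analysis, the synopsis names only a "relative frequency including the two-sided 95% confidence interval according to Wilson". Section 11.4 repeats that and explains that Wilson's interval was chosen because it performs well against the alternatives. It then adds that "the rate of metabolic CR will be estimated using the Kaplan-Meier method and the 95% Greenwood confidence interval", in order "to take into account a potential influence of censored values", for both the ITT and the PP population.

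Section 11.6 defines event times for PFS and OS only; for OS it reads "Calculated from start of therapy up to the time of death". There is no counterpart for metabolic CR.

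On missing results, Section 11.1 expects some: "Assuming a drop-out rate of 10%, 50 patients will be available for final assessment of the primary endpoint". Section 5.5.1 says that for patients who leave early "a withdrawal examination at least with respect to the primary endpoint should be carried out", subject to the patient's consent. Section 11.3 puts everyone who received any protocol treatment into the ITT population. No section says how a treated patient without a week-18 PET enters either estimate.

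**The concern.** Kaplan-Meier needs a time at which each event occurs and a time up to which each event-free patient was observed. Here each patient has one reading. A CR seen at week 18 began at some unknown earlier time. A patient scanned and found not in CR has a known outcome and is not censored. The only patients for whom something is missing are those never scanned, and censoring them assumes they would have responded at the same rate as the rest. Section 5.5.1 lists lack of efficacy, progression and intolerable adverse events among the reasons for withdrawal, so that assumption is doubtful and probably flatters the rate.

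What is at stake is how the primary result is read. This is the only device in the protocol described as dealing with incomplete observation of the primary endpoint. A reader who sees the Kaplan-Meier rate agree with the scanned-only rate could conclude that missing results had been examined and did not matter, when the agreement is built in.

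**Working it through.** **Inputs.** From Section 11.1: 93 recruited, 79 after stage shift, 55 starting therapy with PET-positive lymphoma, 50 assessed, 60% CR. Hence 30 CR, 20 scanned non-CR and 5 unscanned.

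**The protocol's own figures.** 93 × 0.85 = 79.05; 79 × 0.70 = 55.3; 55 × 0.90 = 49.5, about 50. The asymptotic half width is 1.96 × √(0.6 × 0.4/50) = 13.6 points, stated as about 13.5. Both reproduce.

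**Kaplan-Meier at a nominal week 18.** The 5 unscanned patients are censored before week 18, leaving 50 at risk with 30 events at one time.
- S = 1 − 30/50 = 0.40, so the CR rate is 60.0%.
- Greenwood SE = 0.40 × √(30/(50 × 20)) = 0.0693; interval 60.0% ± 1.96 × 6.93 points = 46.4% to 73.6%.

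With a single event time, Greenwood's variance reduces to p(1 − p)/n, so this is exactly the asymptotic interval for 30/50.

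**Proportions with Wilson intervals.**

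| Rule for the 5 unscanned | Rate | 95% interval |
|---|---|---|
| left out | 30/50 = 60.0% | 46.2% to 72.4% |
| non-CR | 30/55 = 54.5% | 41.5% to 67.0% |
| CR | 35/55 = 63.6% | 50.4% to 75.1% |

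Kaplan-Meier matches the first row. It gives 54.5% only if the unscanned patients are kept at risk past week 18, that is, not censored.

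**Other numbers unscanned.** With 2 of 55 unscanned and 32 CR: 32/53 = 60.4% against 32/55 = 58.2%, a gap of 2.2 points. With 8 unscanned and 28 CR: 28/47 = 59.6% against 28/55 = 50.9%, a gap of 8.7 points.

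**Withdrawal examinations.** Suppose all 5 drop-outs are examined at withdrawal, *c* are in CR, and the others are censored then. Kaplan-Meier gives 1 − 0.40 × (1 − *c*/55), from 60.0% (*c* = 0) to 63.6% (*c* = 5). The observed proportion is (30 + *c*)/55, from 54.5% to 63.6%. For *c* = 2 the figures are 61.5% and 58.2%. Patients examined and found not in CR are still credited with a chance of CR.

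**If actual scan dates were used.** The protocol does not state this coding; the case is conditional. Assume scans spread evenly over *D* days, independent of response, with scanned non-CR patients censored on the scan day. The expected daily hazard is 0.6 divided by the fraction of the window remaining, counted in days. The end-of-window estimate is approximately 1 − ∏(1 − 0.6/(D − j)), j = 0 to D − 1.
- D = 5: 1 − 0.88 × 0.85 × 0.80 × 0.70 × 0.40 = 83.2%; after three days, 1 − 0.88 × 0.85 × 0.80 = 40.2%.
- D = 15 (the ±1 week window): about 36% at mid-window, 78% one day before the end and 91% at the end. Simulation with exactly 30 CR among 50 agrees.

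The true rate is 60% throughout, so scan order alone moves the figure. If non-CR patients stay at risk to the end of the window, the end value returns to 60.0%.

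**The case against.** The strongest reply is that the estimate is a harmless supplement. The Wilson analysis comes first and is the only one in the synopsis, the trial is descriptive, and nothing depends on the Kaplan-Meier figure. At a nominal time it is close to the scanned-only sensitivity analysis recommended here: the point estimates are identical and the limits differ by 0.2 and 1.2 points. All of that stands and limits the weight of the point.

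It is also fair to say that the 5.5-point gap is not caused by Kaplan-Meier. It is the difference between two rules for missing results, and a Wilson interval on 50 patients shares it. The criticism is that Kaplan-Meier is offered as the remedy and adopts one of those rules without saying so. The same rate labelled as scanned-only would not mislead.

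The scan-date values rest on a coding the protocol does not mention, and the endpoint wording points to a nominal time. They show what an unspecified method could produce, not what is planned.

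Finally, Section 11.4 leaves details to a SAP to be finalised before data base lock, and withdrawal examinations will supply some readings. Neither rescues the method. Any coding that censors the unscanned patients credits them with the response of others, and a withdrawal examination is still one reading at a date set by withdrawal, not by the onset of CR.

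**Conclusion.** The concern holds. A Kaplan-Meier estimate of a status read once per patient has no event times to use and cannot do the job Section 11.4 gives it. Read at a nominal week 18, it repeats the scanned-only rate (60.0%) with an interval that the same section passes over in favour of Wilson's. It stands 5.5 points above the rate with unscanned patients as non-CR (54.5%), against a planned half width of about 13.5 points.

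The size depends on the protocol's assumptions of 55 starting, 50 scanned and 60% CR, and on a missing-as-non-CR rule that the protocol does not state. The defect itself does not depend on those numbers. It should be corrected before data base lock, but it does not undermine the main Wilson analysis.

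**What to change.** In Section 11.4, or in the SAP it refers to, delete the Kaplan-Meier/Greenwood estimate of metabolic CR and keep those methods for PFS and OS. State instead:

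- The primary estimate is the metabolic CR rate with a Wilson 95% interval over all treated patients with PET-positive lymphoma at baseline. Patients with no evaluable PET at week 18 or at a withdrawal examination, or with progression before it, count as non-CR.
- Sensitivity analyses give the rate among scanned patients only and the rate with missing results counted as CR.

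This takes about two sentences and needs no new data. The cost is that the headline rate may be a few points lower than a scanned-only rate.
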